8.7 Sample Collection and Processing

Blood will be obtained by direct venipuncture in the arm, or via an indwelling cannula. Subjects may use up to 1 indwelling cannula in each study period. If the cannula fails to work (i.e. it becomes clogged), the remaining samples will be taken by direct venipuncture. If catheter will be used, the residual volume in the dead space will be washed with saline each time before taking the sample. Subjects who use cannulas will have them removed:

- After the last blood sample collection of confinement (not later than the 24 hour time point);
- If deemed necessary by clinic staff (for any reason);
- If subject requests removal.

Blood sample collection times will be recorded on the appropriate source documents and reported for each subject.

[figure not shown]
Number of Samples	17 samples from 17 time points in each study period
Total Volume of Blood (for all periods, including approximately 29 mL for pre- and post-study procedures and 44 mL for laboratory testing at check-in for each study period)	Approximately 345 mL of blood
Type of Vacutainer	Pre-chilled K ₂ EDTA Vacutainer®, 4 mL
Blood Sampling Time Points ♦	Pre-dose (0 hour) and at 1, 2, 3, 4, 5, 6, 7, 8, 9, 10, 12, 16, 20, 24, 36 and 48 hours after nifedipine dosing in each study period.

The blood samples collected from each subject will be processed and divided into 2 aliquots. The blood sampling and processing will be performed as per the laboratory directive.

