13.0 PHARMACOKINETIC AND STATISTICAL ANALYSIS

13.1 Pharmacokinetic Analysis Data Set

The data from the following subjects meeting one of the criteria will be included in the final PK and statistical analysis:

1. Subjects who complete at least two study periods with both test and reference administered alone; or two study periods with the same product administered with and without PPI.
2. Subjects who have missed samples that have been pre-determined prior to the start of bioanalytical analysis to not significantly impact the overall outcome of the study.

Data from subjects who were dismissed or withdrew due to AE(s) will not be included in the PK and statistical analysis. The data for these subjects will be presented separately.

Any decision for excluding data from the final data set will be provided with a detailed explanation and will be properly recorded and dated.

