13.3 Analysis of Data

Pharmacokinetic, pharmacodynamic and statistical analysis will be performed on all data from all subjects in the final data set.

The PK, PD and statistical analysis will be performed at BPSI using SAS® Version 9.4. The PK, PD and/or statistical analyses outlined in this protocol may be altered with appropriate justification.

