13.3.1 Pharmacokinetic Analysis

Pharmacokinetic parameters will be calculated using non-compartmental analysis (NCA) method. The following PK parameters will be estimated (where possible) for nifedipine and included in the PK and statistical analysis for the subjects in the final data set:

AUC_{inf} :	Area under the concentration-time curve from time zero to infinity, calculated as $AUC_t + C_{last}/\lambda$, where C_{last} is the last measurable concentration.
AUC_t :	Area under the concentration-time curve from time zero until the last measurable concentration or last sampling time t , whichever occurs first. AUC_t is estimated using the trapezoidal method.
C_{max} :	The maximal observed plasma concentration.
$T_{1/2}$:	Terminal elimination half-life, estimated as $\ln(2)/\lambda$.
T_{max} :	Time when the maximal plasma concentration is observed.
λ :	Terminal elimination rate constant, estimated by linear regression analysis of the terminal portion of the \ln -concentration vs. time plot.

If nifedipine concentration in the subject's plasma before administering any nifedipine (i.e. pre-dose) in any given period is less than or equal to 5% of the C_{max} value for that subject in the given period, then the subject's data without any adjustments can be included in all PK measurements and calculations. If the pre-dose value is greater than 5% of the C_{max} , data from that subject may be dropped from the PK and statistical analysis based on the assessment of the pharmacokinetic scientist and sponsor. Data for subjects dropped due to higher than 5% of C_{max} pre-dose concentrations will be included in a separate appendix in the final study report.

During PK and statistical analyses, drug concentrations below the lower limit of quantitation (BLQ) of an assay will be considered as zero except when they occur between two non-BLQ concentrations where they will be considered as missing during PK calculations and estimations.

Missed samples and non-reportable concentrations (e.g. quantity not sufficient) from the analytical laboratory will be treated in the pharmacokinetic analysis as if they have not been scheduled for collection.

The λ , $T_{1/2}$, and AUC_{inf} parameters will not be estimated for plasma concentration-time profiles where the terminal linear phase is not clearly defined.

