For subjects with missing or non-reportable nifedipine concentrations for three or more of the last samples, only the C_{max} and T_{max} will be presented and included in the statistical analysis. Other PK parameters will not be reported.

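### Section 13.3.1 keeps Cmax and Tmax from profiles that lose their tail, with no limit on the number of samples lost and no check that the peak was passed.

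*Combined protocol and SAP*

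**What the plan says.** All references are to the combined protocol and SAP.

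- Section 8.7 schedules "17 samples from 17 time points in each study period". The last three fall at "24, 36 and 48 hours after nifedipine dosing in each study period".
- Section 13.3.1 defines Cmax as "The maximal observed plasma concentration", with no condition that a fall follows it. Missed and non-reportable samples "will be treated in the pharmacokinetic analysis as if they have not been scheduled for collection".
- The tail rule in the same section says that, when concentrations are missing or non-reportable "for three or more of the last samples, only the C_{max} and T_{max} will be presented and included in the statistical analysis". The remaining parameters are not reported.
- Section 13.1 opens with "The data from the following subjects meeting one of the criteria will be included in the final PK and statistical analysis". The first criterion is "Subjects who complete at least two study periods with both test and reference administered alone", or the same product with and without the PPI. The second admits subjects whose missed samples were judged, before bioanalysis, not to affect the outcome materially; it gives no numerical limit.
- Under Section 13.3, "statistical analysis will be performed on all data from all subjects in the final data set".
- Some profiles are removed or reviewed elsewhere. Section 13.1 excludes withdrawals and dismissals for adverse events. Section 12.1.1 leaves non-compliance dismissals unassayed. Section 7.7 sends emesis and diarrhea to a case-by-case decision.

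**The concern.** The tail rule has a lower trigger and no upper bound. It treats a profile as too incomplete for AUC, yet orders its Cmax and Tmax into the ANOVA however early the profile stops. For an extended-release tablet whose concentrations are still climbing, the highest observed value is simply the last sample drawn.

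Cmax is one of three metrics judged against 80.00–125.00% in all four comparisons. Cutting a profile short before its peak can only lower the observed Cmax and make Tmax earlier, so the affected arm is biased downwards. The outlying value also inflates the residual variance that all four confidence intervals share. By contrast, the gastric pH data set in Section 13.2 does set a minimum follow-up, of 4 h.

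**Working it through.** **1. The plan's own figure.** Section 7.1 gives a CV of 27%, a ratio of 1.08, limits of 80–125%, 52 completers and at least 80% power. The within-subject variance is ln(1 + 0.27²) = 0.070, so the SD is 0.265. For a 2×2 crossover, SE = 0.265 × √(2/52) = 0.052 with 50 df. Exact power for the two one-sided tests is 87.0%, so the stated figure holds.

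**2. What the trigger covers.** The schedule is 0, 1, 2, 3, 4, 5, 6, 7, 8, 9, 10, 12, 16, 20, 24, 36 and 48 h.

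| Last samples missing | Last retained |
|---|---|
| 3 | 20 h |
| 5 | 12 h |
| 8 | 8 h |
| 10 | 6 h |
| 12 | 4 h |
| 15 | 1 h |

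Every row meets the trigger, and in every row Cmax and Tmax are kept.

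**3. Whether anything else removes such a profile.** The Section 13.1 criteria are alternatives. A subject who meets the first is in the data set whatever is missing in another period; the missed-sample judgement is a second way in, not a filter. Section 13.3 then analyses all of that subject's data. After the exclusions listed above, two sources remain: mid-period departures for other reasons, and lost or non-reportable samples.

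**4. Which arms.** Lost samples can occur in any period and arm. For a subject who leaves mid-period and enters through the first criterion, the Section 5.3 sequences give:

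| Sequence | Qualifies after two periods? | Partial Period 3 admitted | Partial Period 4 admitted |
|---|---|---|---|
| 1 (A, B, C, D) | Yes (A, B) | C | D |
| 2 (B, C, D, A) | No | – | A |
| 3 (C, D, A, B) | No | – | B |
| 4 (D, A, B, C) | No | – | C |

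Arm C has two routes and each other arm has one. This counts routes, not events.

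**5. How low the value can be.** The documents give no profile, so this step is assumed: zero-order input over 8–24 h, a 1 h lag and a half-life of 2–9 h (Section 3.2 puts the mean below 10 h). Let k = ln 2 / half-life, t = time since the lag and D = input duration. Concentration is then proportional to 1 − exp(−kt) up to D and declines at rate k afterwards. Observed maximum as a share of the true Cmax:

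- data to 4 h: 25–69%
- data to 6 h: about 39–88%
- data to 8 h: 50–97%
- data to 20 h: about 93–100%

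**6. Effect on C/A.** Take 52 completers plus m Sequence 1 subjects whose Period 3 profile keeps a fraction f of Cmax. The approximate multiplier is f^(m/(52+m)).

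- One profile: 0.65^(1/53) = 0.992; 0.26^(1/53) = 0.975.
- Three profiles: 0.65^(3/55) = 0.977; 0.26^(3/55) = 0.929.

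Simulating the ANOVA with subject, period and arm terms gives the same picture: 0.99–0.98 for one profile and 0.98–0.93 for three. Residual variance rises from 0.070 to at most about 0.091.

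**7. Effect on the conclusion.** Chance that the 90% CI for C/A lies within 80–125%, by simulation, for f from 0.65 down to 0.26 (simulation error is a point or two):

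| True C/A | No truncated profile | One | Three |
|---|---|---|---|
| 1/1.08 | about 87% | about 85% to 74% | about 77% to 36% |
| 1.00 | about 99% | 99% to 98% | 99% to 87% |
| 1.08 | about 88% | 91% to 95% | 94% to 99% |

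**The case against.** The strongest reply is that such cases are rare and already partly handled. Adverse-event withdrawals, the likeliest reason to leave confinement, are excluded. Non-compliance dismissals are not assayed, and emesis and diarrhea are reviewed before bioanalysis. Section 13.1 allows documented exclusions and Section 13.3 allows justified changes. Three truncated arm C profiles would mean about 18% of Sequence 1 (3 of 16–17 subjects) leaving within hours of the Period 3 dose for other reasons, with nothing offsetting elsewhere. Much of this stands, and it is why the point is minor. It does not repair the rule: those discretionary provisions are not prespecified limits, and the text as written orders the value in.

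A reader might infer from the sequences that truncated profiles will fall mostly on arm C. The documents do not support that. The count of two routes to one applies only to mid-period dropouts who enter through the first criterion. Lost samples have no arm preference, and the second criterion could admit partial Period 3 profiles from Sequences 2–4. Sampling times and the 48 h post-dose confinement are the same in all arms, and no missing-sample rate or Tmax by arm is given.

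A reader might also infer a loss of power. That appears clearly only if the true C/A is below 1. The 1.08 in Section 7.1 is a Test-to-Reference ratio, and Section 3.1 leaves open whether the generic amplifies or reduces the pH dependence.

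**Conclusion.** The gap is real and minor. As written, Section 13.3.1 admits a Cmax that is too low and a Tmax that is too early whenever a retained profile stops before its peak, and no other section reliably removes it. One arm C profile among about 52 subjects moves C/A by about 1–2%, and three move it by about 2–7%. The residual variance rises from 0.070 to at most about 0.09.

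The consequence has no fixed direction. A conclusion of no interaction becomes less likely if the true ratio is below 1 and more likely if it is above. A claim that arm C is the usual victim, or that power necessarily falls, goes beyond the documents.

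The sizes rest on the assumed release profiles and the assumed number of truncated profiles. The plan allows for 13–14 non-completers (65–66 enrolled less 52), but only those who leave between the dose and the peak for reasons not already excluded count, together with lost samples. If there are none, nothing changes.

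**What to change.** Replace the tail rule in Section 13.3.1 with one that applies by period, since the present text speaks of subjects. When three or more of the last samples in a period are missing or non-reportable:

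- Include that period's Cmax and Tmax only if at least one reportable concentration after the observed maximum shows a decline.
- Otherwise set that period's Cmax and Tmax to missing, list them separately, and keep the subject's other complete periods.
- Keep the existing restriction on the other parameters.

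Add a sensitivity analysis that excludes every Cmax and Tmax from periods meeting the trigger. This covers profiles where an early dip precedes a later, unseen peak.

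A decline condition is preferable to a fixed time cut-off. Under the assumed profiles, a 20 h limit would discard profiles ending at 12 or 16 h whose peak had already been seen, and would keep some at 20 h that hold only about 93% of it.

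The cost is one or two sentences and perhaps a few values lost from the Cmax and Tmax analyses. By the calculation in step 1, power is 85.8% with 50 subjects and 84.5% with 48, still above the stated 80%. No extra subjects or procedures are needed.

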13.3.2 Pharmacodynamic Analysis

Pharmacodynamic (PD) parameters of omeprazole/sodium bicarbonate (i.e. proton pump inhibitors) will be evaluated for all subjects with at least 4 hours pH measurement. The PD parameters include gastric pH, change of gastric pH from baseline.

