SmartPill™ capsules will be administered on Day 2 approximately 30 minutes before nifedipine dosing (Study arm A and B), and on Day 7 prior to dosing of nifedipine and omeprazole/sodium bicarbonate capsules (Study arm C and D).

Gastric pH Time-points	The pH will be measured at 0, 1, 2, 3, 4, 5, 6, 7, and 8 hours after SmartPill™ administration in each study arm. The pH will be monitored continuously for 24 hours post-dose.
Analyte(s) to be measured:	Plasma samples will be assayed for nifedipine using a validated analytical method according to the principles of Good Laboratory Practice.
Pharmacokinetics and Gastric pH:	Descriptive statistics of pharmacokinetic parameters AUC_t , AUC_{inf} and C_{max} , as well as T_{max} , λ and $T_{1/2}$ will be calculated for each study arm group. The descriptive statistics of the gastric pH and change of gastric pH will be calculated for both test and reference products.
Statistical Analysis:	
For Pharmacokinetic Data: Analysis of Variance (ANOVA) for ln-transformed AUC_t, AUC_{inf} and C_{max}, and untransformed T_{max}, λ and $T_{1/2}$. T_{max} will also be analyzed using an additional non-parametric test (Wilcoxon test). The 90% confidence intervals (CI) for the ratios of geometric means for AUC_t, AUC_{inf} and C_{max} will be calculated based on the least square means (LSMEANS) and ESTIMATE of the ANOVA.
 
For Pharmacodynamic Data: Analysis of Variance (ANOVA) for gastric pH and change of gastric pH from baseline will be carried out.

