2.0 TABLE OF STUDY PROCEDURES

Procedure/Activity	Time points						
	Screening	Each Period Check-in	Period 1	Period 2	Period 3	Period 4	Post-Study
ICF	X ^a						
Drugs of Abuse	X	X					
Alcohol Test	X	X					
Cotinine	X	X					
Pregnancy (hCG) Test*	X	X					
Vital Signs (BP, HR, RR and Temperature)	X		X ^b	X ^b	X ^b	X ^b	X
Laboratory Testing	X	X [#]					X
Medical History	X						
BMI	X						
ECG	X						
Inclusion/Exclusion Assessment	X						
Restrictions Compliance Check		X	X	X	X	X	
Physical Exam	X						X
SmartPill™ Administration			X ^c	X ^c	X ^c	X ^c	
Nifedipine ER tablets Dosing (Test)			X ^d		X ^d		
PROCARDIA XL (Ref)				X ^d		X ^d	
omeprazole/sodium bicarbonate capsules Dosing					X ^e	X ^e	
pH Measurement			X ^f	X ^f	X ^f	X ^f	
PK Sampling			X ^g	X ^g	X ^g	X ^g	
Adverse Event Reporting		X ^h	X	X	X	X	X
Meals		X	X ⁱ	X ⁱ	X ⁱ	X ⁱ	

- # Laboratory testing (hematology, serum biochemistry, and urine analysis) at each period check-in for Study arm A and B on Day 1 and for Study arm C and D it will be done at check-in on Day 3.
- a- At screening and prior to any medical screening procedures.
- b- Vital signs measurements (BP, HR, RR and temperature) to be obtained for Study arm A and B, and on Day 7 for Study arm C and D at pre-dose and at 4, 12 and 24 hours after dosing nifedipine ER tablets in each study period, and at pre-dose and 1 hour after omeprazole/sodium bicarbonate capsules daily dosing (Day 1 to Day 6) in each study period for Study arm C and D.
- c- SmartPill™ capsules will be administered 30 minutes before dosing nifedipine ER tablets (Study arm A and B), and 30 minutes before dosing nifedipine ER tablets and omeprazole/sodium bicarbonate capsules (Study arm C and D) on Day 7.
- d- Study arm A and B: Nifedipine dosing on Day 2 in each study period
Study arm C and D: Nifedipine dosing on Day 7 co-administered with omeprazole/ sodium bicarbonate in each study period.
- e- Study arm C and D: omeprazole/ sodium bicarbonate capsules dosing for 7 days (Day 1 to 7) in each study period.
- f- pH will be measured at 0, 1, 2, 3, 4, 5, 6, 7, and 8 hours after SmartPill™ administration in each study period.
- g- PK sampling - Pre-dose (0 hour) and at 1, 2, 3, 4, 5, 6, 7, 8, 9, 10, 12, 16, 20, 24, 36, and 48 hours after nifedipine dosing in each study period.
- h- Pre-dose conditions at Period 1 check-in.
- i- Study arm A and B: Meals will be served at approximately 6.5, 10.5, 14.0, 24.5, 28.5, 33.5 and 37.5 hours after dosing.

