13.3.3 Statistical Analysis

Descriptive statistics (min, max, median, mean, standard deviation and coefficient of variability) of all PK parameters will be provided for nifedipine for all study arm groups.

ANOVA including sequence, subjects nested within sequence, period and study arm will be performed on the ln-transformed data for AUC_t , AUC_{inf} and C_{max} and on the untransformed data for T_{max} , λ and $T_{1/2}$.

T_{max} will be analyzed using an additional non-parametric test (Wilcoxon test).

The 90% CI of the ratios of geometric means for AUC_t , AUC_{inf} and C_{max} will be calculated based on the LSMEANS and ESTIMATE of the ANOVA.

The following PK comparisons will be carried out:

- Test with PPI (Study arm C)/Test without PPI (Study arm A)
- Reference with PPI (Study arm D)/Reference without PPI (Study arm B)
- Test with PPI (Study arm C)/Reference with PPI (Study arm D)
- Test without PPI (Study arm A)/Reference without PPI (Study arm B)

For Pharmacodynamic Data:

The descriptive statistics (min, max, median, mean, standard deviation and coefficient of variability) of the gastric pH and change of gastric pH will be calculated for both test and reference products.

Analysis of Variance (ANOVA) for gastric pH and change of gastric pH from baseline will be carried out.

The following gastric pH comparisons will be carried out:

- Study arm C PPI (Day7) – Study arm A (Day2)

- Study arm D_{PPI (Day7)} – Study arm B_(Day2)
- The comparison of the change between test and reference can be assessed

Additional statistical and alternate tests will be performed if necessary.

Missing data will not be included in the statistical analysis. There are potential two kinds of unbalanced designs for the analysis: (1) unequal number of subjects across groups, (2) missing cells: there are not available data for some subjects. The Type 3 method will be used for the calculation of sums of squares using SAS software. All the fixed effects will be tested using the Type 3 in the ANOVA to detect statistically significant differences ($\alpha=0.05$) if applicable. A mixed effects ANOVA model for gastric pH with fixed factors of sequence, period, and study arm and random effects of subject will be fit. A compound-symmetric or other appropriate covariance structure will be used in the analysis.

The null hypotheses for gastric pH comparisons for different study arms are:

- For the comparison of Study Arm A and Study Arm C

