 - H01: There is no difference between Study Arm A and Study Arm C
 - H11: There is a difference between Study Arm A and Study Arm C
- For the comparison of Study Arm D and Study Arm B
 - H02: There is no difference between Study Arm D and Study Arm B
 - H12: There is a difference between Study Arm D and Study Arm B
- For the comparison of Study Arm A and Study Arm B
 - H03: There is no difference for the change of median between Study Arm A and Study Arm B
 - H13: There is a difference for the change of median between Study Arm A and Study Arm B

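### The third gastric pH hypothesis (H03/H13) compares the two arms without PPI, and the baseline for change in gastric pH is undefined

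*Combined protocol and SAP*

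**What the plan says.** **Measurement.** The pH capsule is swallowed once per period. For the arms without PPI, the Synopsis says "SmartPill™ capsules will be administered on Day 2 approximately 30 minutes before nifedipine dosing (Study arm A and B"); for the PPI arms, "and on Day 7 prior to dosing of nifedipine and omeprazole/sodium bicarbonate capsules (Study arm C and D"). Section 2.0 (footnote e) specifies "omeprazole/ sodium bicarbonate capsules dosing for 7 days (Day 1 to 7) in each study period" for arms C and D, and footnote f adds "pH will be measured at 0, 1, 2, 3, 4, 5, 6, 7, and 8 hours after SmartPill™ administration in each study period".

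**Purpose.** The SmartPill part of Section 3.3 says the pH data are to confirm that subjects respond to the PPI and to establish how far seven days of dosing raises gastric pH.

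**Endpoints and comparisons.** Section 13.3.2 says: "The PD parameters include gastric pH, change of gastric pH from baseline". The Synopsis and Section 13.3.3 plan an ANOVA of both parameters. Section 13.3.3 then lists three pH comparisons: C (Day 7) minus A (Day 2), D (Day 7) minus B (Day 2), and "The comparison of the change between test and reference can be assessed".

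**Hypotheses.** At the end of Section 13.3.3, H01 concerns A and C, and H02 concerns D and B. The third is "H03: There is no difference for the change of median between Study Arm A and Study Arm B", with H13 as its alternative.

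**The concern.** Two things do not fit together.

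First, the only pH hypothesis that sets test against reference is written for arms A and B. Section 5.3 defines both as nifedipine without PPI. The comparison listed just before the hypotheses concerns the change with each product, and it follows directly on C−A and D−B. No stated hypothesis compares C with D, or C−A with D−B.

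Second, change from baseline is a named endpoint with its own ANOVA, but baseline is never defined. A programmer could reasonably take the 0-h reading of each period. In A and B that reading is untreated; in C and D it is not.

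The study asks whether the PPI interaction depends on the formulation. A reader of the C/A, D/B and C/D exposure ratios will want to know whether gastric pH was raised to a similar extent with both products. H03, followed as written, does not inform that. An undefined baseline also leaves the choice open until the data are seen, since Section 13.3 lets the analyses be altered with justification.

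**Working it through.** The documents give no pH effect size, standard deviation or power, so there is no stated figure to reproduce. The check traces the schedule and then the contrasts.

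**Step 1: is there a reading before PPI in C or D?** There are seven daily doses (Section 2.0, footnote e). The capsule is swallowed 30 minutes before the Day 7 dose (footnote c; Appendix A example: 7:00 and 7:30 AM).

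- PPI doses before the 0-h reading: 7 − 1 = 6.
- Time since the Day 6 dose, at 24-h dosing: 24 − 0.5 = 23.5 h.
- Section 3.2 puts loss of the omeprazole effect at 3 to 5 days after stopping, that is 72 to 120 h.

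So the 0-h reading in C and D is taken on treatment, and those periods contain no pre-PPI pH.

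**Step 2: are A and B valid untreated controls?** The washout is at least 14 days, against 3 to 5 days for loss of effect. Yes.

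**Step 3: what does each contrast estimate?** Let m be the untreated mean pH, δT and δR the mean rise after 0 h on Day 7 with test and reference, and f the share of that rise already present at 0 h. Period effects are left out because the model adjusts for them.

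| Contrast | Expected value |
|---|---|
| C−A (H01) | (m + δT) − m = δT |
| D−B (H02) | (m + δR) − m = δR |
| A−B (arms in H03) | m − m = 0, whatever δT and δR are |
| (C−A)−(D−B) | δT − δR |
| Change from 0 h, C against A | (1 − f)δT |
| Change from 0 h, D against B | (1 − f)δR |

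The third row holds for any summary, median or mean, change or absolute: a statistic computed from A and B alone contains neither δT nor δR. Rearranged, (C−A)−(D−B) = (C−D)−(A−B), so H03 keeps A−B and leaves out C−D.

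The last two rows are only what the Day 7 dose adds. The documents do not give f; Step 1 implies that it is above 0.

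**Step 4: illustration.** A simulation used 52 subjects, 2,000 runs per scenario, and paired t-tests at two-sided 0.05. Assumed values, none from the documents except the number of subjects: untreated pH 1.8; PPI rise 3 units with test and 3 or 2 with reference; SD 0.5 between subjects, 0.5 between periods and 0.4 per reading; no added effect of the Day 7 dose (f = 1). A against B was tested on absolute pH after 0 h.

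| Test | Rejected, rises 3 and 3 | Rejected, rises 3 and 2 |
|---|---|---|
| C−A | 100% | 100% |
| D−B | 100% | 100% |
| Change from 0 h, C against A | 4.55% | 5.0% |
| Change from 0 h, D against B | 4.55% | 4.35% |
| A against B | 4.65% | 4.8% |
| (C−A) against (D−B) | 4.75% | 99.95% |

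A against B rejects at about the 5% level whether or not the products differ. The change-from-0-h rows stay near 5% because f was set to 1; a smaller f would raise them.

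**The case against.** **The plan already estimates the PPI effect.** C−A and D−B are within-subject comparisons against untreated periods, and H01 and H02 test them. This stands. A reader might infer that the pH analysis cannot show the PPI effect at all; the documents do not support that.

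**Baseline may mean the matched no-PPI arm.** Read in order, the three listed comparisons suggest that change means C−A and D−B, and that the third is (C−A) against (D−B). On that reading no PPI effect is subtracted away. This is a fair reading and probably the intended one, but it is nowhere stated, the third comparison is only permissive, and on this reading H03 is the wrong hypothesis.

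**Change from 0 h might still show something.** Section 3.3 says the sodium bicarbonate in the capsule raises gastric pH, so the Day 7 dose could produce a within-period rise. This stands too: a reader should not conclude that such a change would be near zero. It would still not be the seven-day effect.

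**H03 may be a labelling slip.** Section 9.1 uses A and B as codes for the test and reference products. That is plausible, but H03 names study arms, and H01 and H02 just above use the same labels for arms. An analyst following the text would compare A with B.

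**Nothing primary depends on pH.** This stands. The PK comparisons, the 80.00–125.00% limits and the PK data-set rules make no use of a pH result.

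**Conclusion.** H03/H13 is wrong as written. It compares the two arms without PPI, cannot show whether the PPI-induced pH change is the same with test and reference, and does not match the third comparison in its own section. This follows from the arm definitions, given that the 14-day washout removes carry-over as Section 3.2 expects; it does not depend on the simulated values.

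The missing definition of baseline is a second, conditional defect. If baseline is taken as the Day 7 0-h reading, the change shows at most the added effect of the Day 7 dose. If it is the matched no-PPI period, the endpoint is sound and only H03 needs repair. How much would be lost on the first reading cannot be stated, because the documents give no on-treatment pH.

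The reach is limited to a supportive pharmacodynamic analysis. H01 and H02 still answer whether, and by how much, the PPI raised gastric pH. A reader might infer that the PK or bioequivalence conclusions are undermined, or that an extra pH measurement is required; neither follows.

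**What to change.** - In Section 13.3.2 and the Synopsis, define change in gastric pH as the within-subject difference from the matched no-PPI period: C−A for test and D−B for reference. Name the per-period pH summary used, and state that the Day 7 0-h reading is not a baseline.
- In Section 13.3.3, keep H01 and H02 on absolute pH. Replace H03/H13 with the hypothesis that the C−A change equals the D−B change.
- Estimate it in the planned mixed model, which already has study arm as a fixed factor, with coefficients −1, +1, +1, −1 on arms A, B, C, D. Report the estimate with a confidence interval, because failing to reject no difference does not show equality.
- Make the third listed comparison definite, so that it matches the new hypothesis.

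The cost is a few sentences and one contrast. There is no new measurement, visit or subject, and no data already planned are lost.
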